2.1 Background Information and Relevant Literature

Sleep duration in America has gradually declined over the last four decades, with current average sleep duration being of approximately 6 hours¹⁸. Parallel to this decline, African Americans (AAs) have the

CONFIDENTIAL

This material is the property of the NYU School of Medicine and Langone Medical Center. Do not disclose or use except as authorized in writing by the study sponsor

highest prevalence of long (≥ 9 h) and short sleep (≤ 6 h)⁶¹⁻⁶³, within the intervals commonly associated with morbidity and increased AD-risk⁶⁸⁻⁷⁰. AAs take longer to fall asleep¹⁸⁻²³, have lower sleep efficiency and have consistently shown to spend a smaller proportion of time in deep stages of non-REM (NREM) (also called slow wave sleep [SWS])^{19;20;23-28;32}. Possible mediators underlying these racial differences in sleep include age, sex, obesity, psychosocial factors, health care behaviors and medical disorders^{21;23;27;71-76}. A meta-analysis designed to estimate the magnitude of these variations in sleep, showed that racial/ethnic differences in sleep duration and continuity were moderated by the factors underlined above²³, while only psychosocial stressors (measured as perceived discrimination)^{20;21;26} were partially associated with the decreases in SWS duration, suggesting that race still remained an important independent risk factor for decreased SWS among AAs. A recent study confirmed this finding showing that decreased SWS duration was associated with an increased percentage of African ancestry (%AF)³⁹ even after adjusting for several demographic, socioeconomic and clinical covariates. Further replication is warranted, but African ancestry has also been associated to increased risk for hypertension⁷⁷ and diabetes⁷⁸ both of which have been linked with reductions in time spent in SWS^{79;80}.

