
Ambulatory home monitoring for OSA followed by actigraphy:

Subjects will be asked to monitor their sleep using sleep logs during one week. On the first night, OSA will be monitored using a WatchPAT (*Itamar Medical, Tel Aviv, Israel*) (Figure 8). We have experience using WatchPAT in AAs with very low failure rate (less than 1%). This self-applied device measures peripheral arterial volume changes using a finger-mounted plethysmograph. The information is collated

CONFIDENTIAL

This material is the property of the NYU School of Medicine and Langone Medical Center. Do not disclose or use except as authorized in writing by the study sponsor

with pulse oximetry and is further analyzed using an automated algorithm. This algorithm associates arousals with measurement of O₂Sat to determine respiratory effort-related arousals showing excellent sensitivity and specificity for identification of OSA, defined as AHI4% \geq 5 on full NPSG²²⁴. After automated analysis, all raw data and results are reviewed by [name]. Only subjects with an AHI4% $<$ 15 and AHI4% $>$ 5 with Epworth $<$ 10 will be invited to participate. Those cases with suspicion of OSA will be reviewed by [name] and [name]. If OSA is confirmed, they will be excluded and referred to a sleep specialist. Actigraphs (AMI, Ardsley, NY) (Figure 9) with off-wrist detection and a sleep diary will be provided to the subjects to use for the 7 days following the use of the WatchPAT. The purpose will be to record the sleep-wake cycle and provide estimates of total sleep time (TST) in the home. Actigraph will also provide bedtimes and wake times for NPSG N1-N2 in accordance with their usual sleep habits.

Figure 8.
WatchPAT

Figure 9. Actigraph

Measurement of Slow Wave Sleep (SWS) characteristics using NPSG:

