Each in-lab NPSG will record sleep as recommended by the AASM²²⁵ as described in our previous work¹⁵⁶. Electrode attachment will be performed between 8-9 PM. Subjects will be then asked to sit quietly and/or read until lights out at their habitual bedtime. NPSG N1 will be for habituation, N2 will be for data collection. Arousal index (AI), sleep staging, TST, sleep efficiency and wake after sleep onset (WASO) during NPSG will be scored by one trained technologist blinded to PET data using standard AASM criteria²²⁵. Participants will go home between N1-2 provided that they wear the actigraph with off-wrist detection, avoid naps or exercise and track their meals. SWS will be scored visually as: 1) TST in SWS in min. (SWS duration); and, 2) %TST spent in SWS (%SWS). SWS measurements will be measured in N2. In addition, we will include: 1) slow wave activity (SWA): absolute SWA (defined as power between 0.5-4.0 Hz during NREM), relative SWA (SWA divided by power across all 0.4-50 Hz). NREM cycles will be defined as stages NREM2-3 of \geq 15 min. terminated by REM or wakefulness of \geq 5 min. Delta power will be averaged relative to the number of epochs. 2) SWS continuity: bouts of SWS will be defined as the duration of consecutive 30 sec. epochs of sleep scored as SWS, terminated by one or more epochs scored as another stage as described in our previous work^{226;227}.

Sleep-dependent Neuropsychological Tests:

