9.1 Study Hypotheses

1. Hypothesis 1.1: poor SWS characteristics (short SWS duration, low %SWS, low relative SWA, low SWS continuity and high AI) at baseline will be associated with high %AF. Hypothesis 1.2: psychosocial factors (*e.g.* perceived discrimination) will partially moderate the above relationships.
2. Hypothesis 2.1: race will be associated with longitudinal increases in the annual rate of AD_{PiB}mask change. Hypothesis 2.2: the effect of race in terms of longitudinal increases in AD_{PiB}mask will be partially explained by poor relative SWA at baseline.
3. Hypothesis 3.1: race will be associated with longitudinal changes in global cognition, memory, executive function and sleep-dependent spatial navigational memory. Hypothesis 3.2: the association of race in terms of cognitive decline will be partially explained by poor relative SWA at baseline. Exploratory Hypothesis: absence of improvement in sleep dependent memory consolidation at baseline will be associated with longitudinal decreases in global cognition, memory and executive function.

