9.3 Statistical Methods

General considerations: we will incorporate standard techniques such as omnibus tests and appropriate adjustments to significance (α) levels (*e.g.*, Bonferroni correction) for *post-hoc* contrasts to control for multiple comparisons. Both selection and attrition biases might occur. Appropriate techniques (*e.g.*, Heckman 2-stage approach (GEE Probit Model)^{254;255} and Monte Carlo (EM algorithm)²⁵⁶ will be used to address biases or missing data. Attributes of those who withdrew to follow-up will be contrasted with completers to determine sources of attrition biases. Since only two time points will be analyzed, we will use linear regression models with the annual rate of amyloid change as dependent variable. Significance will be defined by $p < .05$ where p will be Bonferroni corrected when testing *post-hoc* contrasts.

- **Hypothesis (1)**: H1.1) for %AF associations, linear regression models, with each of SWS characteristics as the dependent variable, will be regressed on %AF controlling for age, sex, BMI, AHI, TST, sleep efficiency and WASO. H1.2) This model will test interaction by including the best SWS predictor as dependent variable, the psychosocial factor as a classification factor, %AF and the term created as the cross product of psychosocial factors and %AF.
- **Hypothesis 2-3 (H2-3)**: First we will calculate the associations between race and AD_{PiB}mask represented both as binary (AA *vs.* white) and numeric (%AF). Further analyses will use the representation (s) of race significantly associated with amyloid burden. Second, we will use hierarchical

CONFIDENTIAL

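### H1.1 adjusts every SWS outcome for TST, sleep efficiency and WASO and plans no model without them, so the ancestry association that Aim 1 describes is not estimated

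*Combined protocol and SAP*

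**What the plan says.** Section 9.3 gives H1.1 a single linear model per SWS characteristic, regressed on %AF "controlling for age, sex, BMI, AHI, TST, sleep efficiency and WASO". Section 9.1 lists the outcomes as "poor SWS characteristics (short SWS duration, low %SWS, low relative SWA, low SWS continuity and high AI) at baseline".

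Section 6.1 says where the covariates come from: "Arousal index (AI), sleep staging, TST, sleep efficiency and wake after sleep onset (WASO) during NPSG will be scored by one trained technologist". It also says "SWS measurements will be measured in N2", night 1 being for habituation, and defines the two visually scored outcomes in terms of TST: "SWS will be scored visually as: 1) TST in SWS in min. (SWS duration); and, 2) %TST spent in SWS (%SWS". A second TST exists, because home actigraphy is to "provide estimates of total sleep time (TST) in the home". Section 9.3 does not say which TST enters the model.

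Section 3.1 states Aim 1 as whether %AF is associated with short SWS duration and poor SWA in older African Americans, controlling for psychosocial factors. It mentions no adjustment for other sleep measures. The psychosocial factors are not in the H1.1 covariate list; they appear only as moderators in H1.2.

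**The concern.** TST, sleep efficiency and WASO cannot cause genetic ancestry, so they are not confounders in the usual sense. They are sleep phenotypes recorded alongside the outcome, and three overlaps follow.

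- SWS duration is a component of NPSG TST. Holding TST fixed can shrink the %AF slope even if ancestry affects no other sleep stage.
- %SWS already has TST as its denominator.
- SWS continuity and arousal index are closely related to WASO and sleep efficiency.

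The H1.1 coefficient therefore answers a narrower question than Aim 1: whether ancestry relates to SWS beyond the amount and continuity of sleep. Without a reduced model, a null could mean no ancestry association, or an association shared with sleep amount or fragmentation, and the plan could not tell these apart. Hypotheses 2-3 enter covariates in hierarchical blocks; H1.1 does not.

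**Working it through.** **Inputs from section 9.2:** detectable correlation 0.20, power 80%, 5% level, 200 complete subjects, expected correlation 0.33. Two-sided testing is my assumption.

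**Inputs not in the documents, so assumed:** a = correlation of %AF with a sleep covariate; b = correlation of that covariate with SWS. Signs are set so that ab>0 means the covariate and the ancestry effect run in the same direction.

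**Step 1, the plan's own figure.** Power = Φ(atanh(r)·√(n−3−k) − 1.960), with k covariates. For r=0.20, n=200, k=0: 0.2027 × 14.036 = 2.845, and Φ(0.885) = 81%. The stated 80% is reproduced. With k=7 it is 79.8%, so lost degrees of freedom are not the problem. (Aim 1 names African Americans, 150 planned; n=150 would give 69%. That is a separate matter and I keep 200 here.)

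**Step 2, one sleep covariate added, r=0.20.** Partial correlation = (r−ab)/√((1−a²)(1−b²)). Share of slope retained = (r−ab)/((1−a²)r). With k=1, √196 = 14.

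Worked case a=0.3, b=0.5: numerator 0.20−0.15 = 0.05; denominator √(0.91×0.75) = 0.826; partial correlation 0.0605; slope retained 0.05/0.182 = 27%; power Φ(0.848−1.960) = 13%.

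| a | b | Slope retained | Power |
|---|---|---|---|
| −0.1 | 0.3 | 116% | 93% |
| −0.1 | 0.5 | 126% | 99% |
| 0 | 0.3 | 100% | 85% |
| 0 | 0.5 | 100% | 91% |
| 0.1 | 0.3 | 86% | 72% |
| 0.2 | 0.3 | 73% | 56% |
| 0.2 | 0.5 | 52% | 38% |
| 0.3 | 0.3 | 60% | 40% |
| 0.3 | 0.5 | 27% | 13% |

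**Step 3, the expected r=0.33.** Unadjusted power is 99.8%. At a=0.3, b=0.5 the partial correlation is (0.33−0.15)/0.826 = 0.218, power is 87%, and 0.18/(0.91×0.33) = 60% of the slope remains. The test mostly survives, but the estimate may not.

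**Step 4, overlap by construction (SWS duration with NPSG TST only).** Let TST = SWS + other sleep, with other sleep unrelated to %AF and to SWS. Let λ be the SWS share of TST variance once %AF is accounted for. The slope retained is 1−λ.

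- For λ = 0.1, 0.3 and 0.5, 90%, 70% and 50% of the slope remains. Partial correlations are 0.190, 0.167 and 0.141, and power at r=0.20 is 77%, 66% and 51%.
- Check at λ=0.5: give SWS variance 1, of which 0.96 is residual; other sleep then has variance 0.96 and TST 1.96 = 1.4². The correlation of TST with %AF is 0.20/1.4 = 0.143 and with SWS 1/1.4 = 0.714. The partial correlation is (0.20−0.102)/√(0.980×0.490) = 0.141, and Φ(0.1424×14 − 1.960) = 51%.
- If other stages fully replace the lost SWS, TST does not move with ancestry and the whole slope is kept.

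**The case against.** The strongest case for the planned model is that asking whether ancestry relates to SWS beyond general sleep quantity and continuity is a sensible question. Section 2.1 motivates it by arguing that the SWS difference is independent of other factors. Aim 1 is itself conditional on psychosocial factors, so calling its target the total association goes too far. This stands, and it is why the planned model should be kept.

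A reader might infer that the protocol itself ties all three covariates to race. It does so directly only for sleep efficiency, where African Americans "have lower sleep efficiency and have consistently shown to spend a smaller proportion of time in deep stages" sleep. Section 2.1 attributes differences in duration and continuity to age, sex, obesity, psychosocial, behavioural and medical factors. Its summary denies an independent difference in duration, and WASO is never tied to race. These statements compare self-identified groups, whereas Aim 1 concerns %AF among African Americans.

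Three further points also stand:

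- If the covariate is home actigraphy TST, the component argument fails for TST.
- Relative SWA is a spectral power ratio, not a part of TST, so overlap by construction does not reach it.
- AHI could be questioned on similar grounds, since section 2.1 discusses both race and OSA and the effect of apnea on SWS. Keeping AHI in the first block is a choice the sponsor should justify.

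Section 3.1 says only how a positive result would be read, so misreading a null is a risk and not a stated intention. None of this supplies the missing model.

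**Conclusion.** The point holds in a limited form. As written, H1.1 never estimates the %AF–SWS association without conditioning on sleep outcomes measured alongside SWS, and its coefficient is not the one Aim 1 describes.

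Two stronger conclusions are tempting and unsupported. One is that the adjustment is known to remove part of the ancestry effect. It may, but with a=0 nothing is lost and power rises, and with an opposite-sign correlation the slope grows. The other is that H1.1 has about 13% power. That figure is one corner of an assumed grid, at the smallest correlation the plan aims to detect.

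What can be said is that at r=0.20 and n=200 the grid runs from about 13% to above the unadjusted 81%. At r=0.33 power is 87% or more on the same grid, while up to 40% of the slope may go. Every figure rests on assumed correlations and two-sided testing.

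**What to change.** Pre-specify H1.1 in two blocks for each SWS outcome and report both:

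1. %AF with age, sex, BMI and AHI.
2. The same, adding TST, sleep efficiency and WASO, interpreted as the association specific to SWS beyond sleep amount and continuity.

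Fix before analysis which block is primary; that is the sponsor's choice. Name the TST source (NPSG night 2 or home actigraphy). State that a null in block 2 alone will not be read as no ancestry association. It would also help to say whether the psychosocial control named in section 3.1 belongs in these models.

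The cost is a short addition to section 9.3 and one extra model per outcome. No new data are needed, and the planned estimate is kept as block 2.

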6.1 Procedures/Evaluations

Clinical evaluation: all subjects will perform a standardized clinical evaluation (UDS 3.0) given to all participants seen at the NYU ADC. The purpose of this clinical evaluation is to establish that subjects are cognitively normal, identify concurrent medications that may act as confounders (*e.g.*, benzodiazepines, trazodone, suvorexant), increase reproducibility of the clinical evaluation, and facilitate collaborative research with NACC (see *Resource Sharing Plan*). Depressive symptoms will be measured using the Geriatric Depression Scale (GDS)^{212;213}. We will add information about: health insurance, annual household income, perceived discrimination (Index of Race-Related Stress [IRRS]-Brief Version B²¹⁴), the Weinstein Noise Sensitivity Scale (WNSS)²¹⁵, the Perceived Stress Scale (PSS)²¹⁶ and the SF36 health behaviors survey²¹⁷ to control for environmental, health and psychosocial factors that might disrupt sleep. In addition, all subjects will undergo complete fasting blood tests (CBC with differential and platelet count, highly sensitive CRP, ESR, total T₃ and T₄^{*}, lipid profile, RPR^{*}, comprehensive metabolic profile with insulin, folate^{*}, homocysteine^{*}, and vitamin B₁₂^{*}, SMA-18, HbA_{1c}, hemogram)). Subjects will then complete the WHICAP battery and the AMNART test⁴. The tests comprising this neuropsychological battery were chosen because unlike the UDS 3.0, they have race-specific norms⁵. We will construct three composite scores for general cognition, memory, and executive function from factor analyses. We will use total recall, delayed recall, and delayed recognition from the Buschke Selective Reminding Test²¹⁸ to construct the memory composite. The executive functioning composite will be created using the Color Trail-Making Test (A and B)²¹⁹, WAIS-R (Wechsler Adult Intelligence Scale-Revised), Similarities, Identities/Oddities subtest of the Mattis Dementia Rating Scale²²⁰, two cancellation tasks and semantic fluency for animals²²¹. All of the above variables, together with phonemic fluency²²¹, the 15-item Boston Naming Test²²², repetition task (high-frequency phrases of the Boston Diagnostic Aphasia Examination[BDAE]²²³; and a comprehension task, will contribute to the composite for general cognition. Means and standard deviations (SD) will be calculated from baseline scores for non-demented WHICAP subjects controlling for age, race and years of education using robust norms. Z-scores for each of the cognitive measures will be averaged to create a composite z-score for each of the three domains. Only subjects diagnosed as cognitively normal with a z-score >-1.25 SD of the mean in general cognition will be invited to participate. The time to complete the WHICAP test battery will range from 45-90 min. On visit 2, prior to the PET/MR scan, subjects will complete the UDS 3.0 cognitive evaluation to facilitate collaborative research with NACC.

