9.2 Sample Size Determination

Power was assessed under the assumption that dropout replacement will allow complete data to be acquired from 200 subjects. Based on the existing literature²³⁻³², the coefficient of variation (CV) of SWS duration is anticipated to be as high as 90% among AA and 40% among whites. Baseline data from 150 AA and 60 whites will therefore provide 80% power at the 5% significance level to detect a mean SWS duration among whites that is at least 28% higher than among AA. Based on PD4, the CV of PiB uptake at baseline is anticipated to be as high as 35% among AA and 25% among whites, providing 80(90)% power at the 5% significance level to detect a mean PiB uptake among AAs that is at least 13%(15%) higher than in whites. For Aim 1, the study will have 80% power at the 5% significance level to detect correlations of magnitude $|r|=0.20$ (the study from Halder et al³⁹ showed an R^2 of 11, implying an even greater correlation of 0.33 can be expected in our study). The multivariable regression analysis will have 80% power to detect SWS characteristics that can explain 3% of the variance in the longitudinal change in AD_{PiB}mask (Aim 2) or cognition (Aim 3) after adjusting for covariates that together explain at least 25% of the variance in AD_{PiB}mask/cognition. The detectable effect of 3% variance explained, implies the study can detect partial correlations of magnitude 0.1 between SWS and the outcomes adjusted for the cofactors. It is noted that the power of the multivariable analyses will improve if the covariates explain >25% of the variance. The study will have 80% power to detect sleep measures that explain 10% of the variance in the AD_{PiB}mask ratio even if the covariates explain a negligible percentage of the variance.

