linear regression, with rate of change of AD_{PiB}mask as the dependent variable and race as independent, adjusting for the matching factors: age, sex, BMI, education and annual income (block 1); ApoE4 and ABCA7 (block 2); DWML volumes, DKI indices and mPFC volume (block 3); and SWS characteristic (*e.g.* relative SWA) (block 4). Other covariates (*e.g.*, psychosocial) will be included in the final models if significantly different between AAs and whites as indicated by unequal variance t tests. Although we anticipate that relative SWA will be the best predictor of longitudinal change in AD_{PiB}mask, the best fitting model will be then replicated with each of the other SWS characteristics not listed before. On a final step, we will test whether the effect of SWS on amyloid deposition is different (*i.e.*, stronger) among AAs. The model would include AD_{PiB}mask change, the binary indicator of race (AA=1 *vs.* white=0) and SWA as described in H1.2. If the interaction is significant, it will imply that the effect of SWA on amyloid varies as a function of race. The sign of the estimated coefficient for this term would indicate whether SWA has a significantly stronger or weaker effect among AA. Exploratory Hypothesis: cognitive z-score change in subjects that show improvement in maze CT will be compared with those that don't show improvement using ANCOVA controlling for age, sex, BMI, race, education and ApoE4 status.

- **Post-hoc analyses**: a subset of *post-hoc* analyses will be performed by controlling by PiB levels at baseline and by splitting the sample into PiB+ and PiB- at baseline and performing a separate analysis for each subset. Stratified analyses will also be performed for men and women, as well as for AAs and whites. In addition, we will formally test the impact of PiB status (defined as PiB SUVR \geq 1.4) on the association of sleep measures with longitudinal increases in AD_{PiB}mask. Although we do not anticipate that sleep or SWS characteristics will change over the follow-up period, *post-hoc* analyses will be performed by assessing longitudinal changes in the sleep measures as correlates and predictors of longitudinal changes in the outcomes measures, using paired sample t-tests to assess the change in outcomes and sleep.

10 Source Documents and Access to Source Data/Documents

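### H1.2 enters scored psychosocial scales as a classification factor with no cut-points, which costs the moderation test power and leaves the grouping open

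*Combined protocol and SAP*

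**What the plan says.** Section 9.1 states Hypothesis 1.2 as one of moderation: psychosocial factors, with perceived discrimination as the example, "will partially moderate the above relationships" between %AF and the slow wave sleep (SWS) measures.

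Section 9.3 gives the model. An SWS measure is the outcome, and the right-hand side holds %AF, "the psychosocial factor as a classification factor" and "the term created as the cross product of psychosocial factors and %AF".

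Section 6.1 lists the instruments. They include "perceived discrimination (Index of Race-Related Stress [IRRS]-Brief Version B"), the Weinstein Noise Sensitivity Scale and "the Perceived Stress Scale (PSS"). Health insurance and household income are collected alongside them.

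For Hypotheses 2 and 3, Section 9.3 brings in psychosocial covariates if they are "significantly different between AAs and whites as indicated by unequal variance t tests". That comparison treats them as numeric.

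No section gives a cut-point, a number of classes, degrees of freedom for the interaction, or a reason for grouping. Section 9.2 gives power for Aim 1 only as a simple correlation, and gives nothing for H1.2.

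**The concern.** A classification factor is a set of groups. To use a stress or discrimination score as one, someone has to divide the scale, and the plan does not say where. Two things follow.

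- **Power.** People who differ widely on the scale but fall in the same group are treated as identical. When the moderating effect changes steadily along the scale, the product term is then measured with error and the test is weaker.
- **Analyst freedom.** With no grouping fixed in advance, the split can be chosen after the results are visible. This holds whatever the effect size.

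H1.2 is a stated hypothesis under a primary aim, so its test should be both efficient and fully specified.

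**Working it through.** **Inputs from the plan.** Section 9.2: "For Aim 1, the study will have 80% power at the 5% significance level to detect correlations of magnitude" 0.20, with 200 complete subjects assumed and 150 + 60 = 210 at baseline. Section 3.1 frames Aim 1 in older African Americans, so n = 150 is also possible.

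**Assumptions (not in the plan).** A two-sided test, normally distributed and independent %AF and score, a linear interaction, and its size.

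**1. The plan's own figure.** With Fisher's z, atanh(0.20) = 0.2027.

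- Required n = ((1.960 + 0.842) / 0.2027)² + 3 ≈ 194.
- Power at n = 200: Φ(0.2027 × √197 − 1.960) = Φ(0.885) = 81.2%.

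The stated 80% is reproduced. It applies to the main %AF–SWS correlation, not to the interaction.

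**2. Effect of a split.** A normal score and its median-split version correlate at √(2/π) = 0.798. For a cut leaving a proportion q below it, the factor is φ(c) / √(q(1 − q)), with c the matching normal quantile. The interaction's partial correlation shrinks by that factor.

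**3. Median split, linear interaction.** A standardised interaction b against unit noise corresponds to a partial r of b / √(1 + b²), so b = 0.23 gives 0.224.

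| Assumed partial r | n | Continuous | Median split | Loss (points) |
|---|---|---|---|---|
| 0.20 (becomes 0.160) | 150 | 69.1% | 49.7% | 19.4 |
| 0.20 | 200 | 81.2% | 61.8% | 19.4 |
| 0.224 (becomes 0.179) | 150 | 79% | 59% | 20 |
| 0.224 | 200 | 89% | 72% | 17 to 18 |

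Simulation agrees. At partial r = 0.20 it gives 66.7% against 49.2% (n = 150) and 78.9% against 60.8% (n = 200). At b = 0.23 it gives about 76% against 58% and 88% against 72%. Together these give losses of roughly 16 to 20 points.

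**4. Other assumptions, n = 150 to 210.**

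- *Other cuts, r = 0.20:* 33/67 loses about 22 to 23 points, 25/75 about 26 to 27, 20/80 about 29 to 31.
- *More equal-sized classes, r = 0.20:* three classes (2 df) lose about 20 to 21 points, four about 23 to 25, five about 27 to 28.
- *Other effect sizes, median split:* r = 0.10 loses about 7 to 9 points, 0.15 about 14 to 18, 0.25 about 13 to 18, 0.30 about 5 to 12, 0.33 about 3 to 8.

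For effects from 0.10 to 0.33 the range is therefore about 3 to 31 points. At r = 0.05, power is about 10% either way and the loss is about 2 points.

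**5. A threshold instead of a line.** If the %AF slope truly switches at the median of the scale, with b = 0.23 up or down, the ranking reverses. Simulated power is about 57% continuous against 72% split at n = 150, and about 70% against 84% at n = 200.

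**The case against.** The strongest reply is that the wording may be loose. A cross product fits a continuous score equally well, and psychosocial covariates are treated as numeric elsewhere in Section 9.3. The same section reuses the H1.2 model for binary race, where a classification factor is the right term. Section 6.1 also collects at least one factor, health insurance, that is naturally categorical. All of this stands, so it cannot be said that the plan intends a data-driven split. But the sentence as written directs grouping, and an analyst who follows it would have to choose the groups.

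The second reply is that a continuous product term is not always better, and the threshold case in the working shows this. The plan does not say which shape it expects. A linear term is the sensible default, not a proven optimum.

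A reader might also infer three stronger points that the documents do not support:

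- *The loss is a fixed 18 to 20 points.* That needs an interaction size and a split that the plan does not state.
- *H1.2 decides whether racial differences in SWS belong to stressors or to ancestry.* Section 3.1 rests the genetic inference on the %AF association after adjustment for psychosocial factors. Nowhere is a null interaction read as evidence for a genetic cause.
- *Interaction tests have the least power in the plan.* Section 9.2 gives no power for any interaction, so no such ranking can be made.

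**Conclusion.** The point holds as a defect in a stated method. Section 9.3 directs that scored scales be used as classes and fixes no classes. If the interaction is linear, a median split costs roughly 16 to 20 points of power for an assumed standardised interaction of about 0.20 to 0.23 at n = 150 to 200. Across the other effects and splits examined the loss is about 3 to 31 points. The open choice of grouping does not depend on any of these assumptions.

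Confidence is high that the wording needs changing and lower in any one power figure. No number in the plan is contradicted. The primary endpoint, longitudinal amyloid increase, is unaffected.

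**What to change.** In Section 9.3, H1.2:

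- Replace the classification-factor wording with *as a mean-centred continuous score*.
- Test the product of centred %AF and the centred score (1 df).
- Present simple slopes of %AF at −1, 0 and +1 SD of the score.
- Keep genuinely categorical factors, such as health insurance, as classes and state their levels.
- Allow a grouped version of a scale only as a sensitivity analysis, with cut-points and degrees of freedom fixed before the data are seen.

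The cost is a few words, with no new data, visits or participants. The one downside is lower sensitivity to a pure threshold effect, which the pre-fixed sensitivity analysis covers.
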